6.1 Information to be collected on screening failures

All patients where informed consent has been given for the pivotal phase (including screening failures), will have the Screening Phase Disposition, Demographics, Inclusion / Exclusion, Informed Consent and Adverse Event (if SAE data has been collected) eCRFs completed.

For screened patients who signed informed consent but are not randomized or entered into the next period of the study (usually starting at visit 1) will have adverse events that are not SAEs followed by the investigator and collected only in the source data.

For all patients who signed the informed consent and are randomized, or who are entered into the next period of the study, will have all adverse events occurring after informed consent recorded on the Adverse Event eCRF page, with the exception of all study endpoints.

The investigator will have the discretion to record abnormal test findings on the Medical History eCRF whenever, in their judgment the test abnormality occurred prior to the informed consent signature. For example: an investigator can determine that an ECG abnormality that was seen on an ECG conducted after informed consent was obtained was a pre-existing condition. This pre-existing condition is then recorded on the Medical History eCRF and not as an adverse event.

6.2 Patient demographics/other baseline characteristics

Patient demographic and baseline characteristic data to be collected on all patients include: information on date of birth (if allowable), age, sex, race and ethnicity.

Relevant medical history/current medical conditions present before signing informed consent will be collected at Visit 1 of the pivotal phase. General medical history will include: HEENT, Neoplastic and Hematological Disorders, Cardiovascular history, including MI history, prior events or disease, hypertension, hyperlipidemia, smoking history, Respiratory, Kidneys and Urinary Tract, Gastrointestinal, Immunological and infectious, Endocrine and Metabolic including history and diagnosis of diabetes and its complications, CNS including psychiatric disorders. Relevant medical history/current medical condition data includes data until signing of informed consent. Where possible, diagnoses and not symptoms will be recorded. Family history for cardiovascular diseases will be collected.

6.3 Treatment exposure and compliance

Study treatment will be administered at the clinic under the supervision of the investigative staff with the dosing record captured within each visit on the Drug Accountability eCRF.

Any medications taken within 30 days prior to the date of screening and after will be recorded on the appropriate Concomitant Medications and or Procedures and Significant Non-drug Therapies eCRF.

This will also apply for the extension phase.

6.4 Efficacy

6.4.1 Primary Efficacy assessment (primary objective)

The primary endpoint is defined as the time to the first adjudication committee confirmed major adverse cardiovascular event (MACE) occurring during the double-blind treatment period of the pivotal phase, which is a composite of CV death, non-fatal MI, and stroke.

An independent adjudication committee that is blinded to treatment assignments will review and adjudicate all clinical events that constitute the primary composite endpoint and secondary endpoints.

In the extension phase no endpoints will be collected. MACE will be recorded as adverse events, using the Adverse Event eCRF. No adjudication of events will be performed during the extension phase. Reporting of Adverse Events is described in [Section 7](#).

[figure not shown]
[figure not shown]
6.4.2 Secondary efficacy assessment (secondary objectives)

All the listed secondary efficacy assessments are for the pivotal phase only unless specified otherwise. Key secondary efficacy assessments will comprise:

- Time to the first occurrence of the adjudication committee confirmed composite cardiovascular endpoint consisting of primary endpoint, and hospitalization for unstable angina requiring unplanned revascularization
- Time to adjudication committee confirmed new onset of type 2 diabetes among those with pre-diabetes at randomization (defined in [Section 4](#)) (time to NOD)

Other secondary efficacy assessments will comprise

[figure not shown]
- Time to first event of, non-fatal MI, stroke and all-cause mortality composite
- Time to all-cause mortality

[figure not shown]
6.4.3 Appropriateness of efficacy assessments

Time to major adverse cardiovascular events and progression to diabetes (new onset diabetes) are well defined and standard clinical events in clinical trials aimed at demonstrating primary and secondary efficacy of investigational agents on clinical endpoints. Secondary endpoints are widely used clinical efficacy endpoints in cardiovascular clinical endpoint trials.

6.5 Safety

Safety and Tolerability Assessments

- Laboratory evaluations (performed during pivotal phase and prediabetes washout)
 - Height, weight and waist circumference (performed throughout full study)
 - Adverse events and serious adverse events, including cardiovascular events, malignancies, and infections (performed throughout full study)
 - Discontinuation due to AEs (performed throughout full study)
 - Hypoglycemia events (performed throughout full study)
 - Injection site reactions (assessed throughout full study)
 - Physical Exam (performed during pivotal phase and prediabetes washout)
- 

- [REDACTED]
- Vitals (assessed throughout full study)
- ECG (performed during pivotal phase and prediabetes washout)

Serious allergies/immunological events (e.g. Anti-canakinumab antibodies), serious infections, and malignancies adverse events will be monitored carefully using adverse/serious adverse events procedure described in [Section 7.1](#) Adverse events and [Section 7.2](#) Serious adverse event reporting during this trial because these adverse events represent hypothetical mechanism of action related risks of canakinumab therapy. During the pivotal phase, these adverse events will be adjudicated by an expert adjudication committee to strengthen data quality and safety conclusions. No adjudication of events will be performed during the extension phase.

6.5.1 Physical examination

A complete physical examination will include the examination of general appearance, skin, neck (including thyroid), eyes, ears, nose, throat, lungs, heart, abdomen, back, lymph nodes, extremities, vascular and neurological. If indicated based on medical history and/or symptoms, rectal, external genitalia, breast, and pelvic exams will be performed.

Information for all physical examinations must be included in the source documentation at the study site. Significant findings that are present prior to signing of informed consent must be included in the relevant Medical History/Current Medical Conditions eCRF. Significant findings after the signing of informed consent, which meet the definition of an Adverse Event, must be recorded on the Adverse Event screen of the patient's eCRF.

Physical examination will also be performed during prediabetes washout but not during main drug dispensing period of the extension phase.

6.5.2 Vital signs

[figure not shown]
Vital signs including BP (3 measurements with the average of all three used for inclusion) and pulse measurements will be assessed per the assessment schedule. In general blood pressure should be taken after the patient has been sitting for five minutes, with back supported and both feet placed on the floor. Systolic and diastolic blood pressure should be measured three times using an automated validated device with an appropriately sized cuff. The repeat sitting measurements should be made at 1 to 2 minute intervals and the mean of the last three measurements will be used. If using the automated device and current cuff sizes available are not large enough for the patient's arm circumference, a sphygmomanometer with an appropriately sized cuff may be used.

Vital signs will also be performed during the extension phase.

Clinically notable vital signs are defined in [Appendix 1](#).

6.5.3 Height, weight and waist circumference

Height in centimeters (cm) or inches and body weight (to the nearest 0.1 kilogram [kg] or pound [lb] in indoor clothing, but without shoes) will be measured. Body Mass Index (BMI) will be calculated as the weight in kg divided by the height in meters squared. Waist

[figure not shown]

circumference should be measured with a flexible tape. For consistency among sites, the position for measuring waist circumference will be at the uppermost border of the right iliac crest (or at the umbilicus if landmarks cannot be palpated). The measure should be recorded while the patient is in the expiratory phase of respiration.

Height, weight and waist circumference will also be performed during the extension phase.

6.5.4 Laboratory evaluations

A central laboratory will be used for analysis of all specimens collected. Details on the collections, shipment of samples and reporting of results by the central laboratory are provided to investigators in the laboratory manual. All patients should be fasting for at least 10 hours prior to having the labs drawn at the scheduled time-points. All screening labs must be reviewed for completeness prior to randomization. Lab results that are missing or unavailable must be repeated prior to randomization.

Laboratory evaluations will also be performed during prediabetes washout but not during main drug dispensing period of the extension phase.

6.5.4.1 Hematology

The following tests are included in the hematology but are not limited to: HbA1c, Hemoglobin, hematocrit, red blood cell count, white blood cell count with differential, and platelet count will be measured.

Hematology will also be assessed during prediabetes washout but not during main drug dispensing period of the extension phase.

6.5.4.2 Clinical chemistry

The following tests are included in the chemistry but are not limited to: hsCRP, eGFR, Estradiol, Fasting Plasma glucose, Blood urea nitrogen, creatinine, CK (CK-MB and troponin-I if CK is >2ULN and there is no underlying etiology for the increase in CK), total bilirubin, AST, ALT, alkaline phosphatase, sodium, potassium, chloride, calcium, phosphorous, total protein, albumin, and uric acid will be measured. FSH, HIV screen, HBsAg and HCV antibody will only be measured at Visit 1 for eligibility purposes.

Clinical chemistry will also be assessed during prediabetes washout but not during main drug dispensing period of the extension phase.

[For Japan only]

[figure not shown]
[In Japan, HBc antibody and HBs antibody will also be measured for Visit 1 eligibility purposes. This is not applicable for the extension phase.]

6.5.4.2.1 Fasting Lipid profile

The following tests are included in the fasting lipid profile but are not limited to triglycerides, total cholesterol, HDL cholesterol, LDL cholesterol, VLDL cholesterol and non-HDL cholesterol. LDL cholesterol, VLDL cholesterol and non-HDL cholesterol will be calculated unless triglycerides > 400 mg/dL in which case only a direct LDL cholesterol assay will be employed.

Fasting Lipid profile will also be performed during the prediabetes washout but not during main drug dispensing period of the extension phase.

6.5.5 Electrocardiogram (ECG)

A standard 12 lead ECG will be performed at baseline (Visit 2), yearly visits, and at the end of study visit. ECG's will be read by a central vendor. Each ECG tracing should be labeled with the study number, patient initials (if applicable), patient number, date, and kept in the source documents at the study site. Clinically significant abnormalities should also be recorded on medical history/ adverse events eCRF page. Any potential endpoints should be recorded on the Clinical Study Endpoint Tracking Form eCRF.

ECG will also be performed during the prediabetes washout but not during main drug dispensing period of the extension phase.

6.5.6 Pregnancy and assessments of fertility

[figure not shown]
[figure not shown]
Neither the pivotal phase nor the extension phase include women of child bearing potential and therefore pregnancy test should be performed on all female study participants to detect unexpected pregnancies. A positive urine pregnancy test requires immediate interruption of study treatment until serum β -hCG is performed and found to be negative. If the serum β -hCG is positive, the patient must be discontinued from study treatment but should continue follow up in the trial. Study treatment can be restarted after completion or termination of pregnancy following discussion with the Sponsor.

[figure not shown]
[figure not shown]
6.5.7 Appropriateness of safety measurements

[figure not shown]
[figure not shown]
Safety endpoints used in this trial are standard endpoints in demonstrating safety of investigational agents in clinical trials. Safety events of special interest, in the following categories, serious infections and malignancies, will be adjudicated by two expert adjudication committees during the pivotal phase. No adjudication of events will be performed during the extension phase. Additionally, canakinumab and canakinumab antibody

[figure not shown]
[figure not shown]

[figure not shown]
[figure not shown]
concentrations will be measured during the pivotal phase due to the hypothetical risk of immune response to the study treatment. These safety events of special interest represent hypothetical risks of canakinumab treatment.

[figure not shown]
[figure not shown]

[figure not shown]
[figure not shown]

[figure not shown]
[figure not shown]

[figure not shown]
[figure not shown]

7 Safety monitoring

7.1 Adverse events

An adverse event is the appearance of (or worsening of any pre-existing) undesirable sign(s), symptom(s), or medical condition(s) occurring after signing informed consent.

Adverse events must be recorded in the Adverse Events CRF under the signs, symptoms or diagnosis associated with them.

Abnormal laboratory values or test results constitute adverse events only if they fulfill at least one of the following criteria they induce clinical signs or symptoms, they are considered clinically significant or they require therapy.

The occurrence of adverse events should be sought by non-directive questioning of the patient during the screening process after signing informed consent and at each visit during the study

Adverse events also may be detected when they are volunteered by the patient during or between visits or through physical examination, laboratory test, or other assessments. Clinically significant abnormal laboratory values or test results should be identified through a review of values outside of normal ranges/clinically notable ranges, significant changes from baseline or the previous visit, or values, which are considered to be non-typical in patient with underlying disease

During the pivotal phase all adverse events, which are no protocol endpoints, must be recorded on the Adverse Events CRF with the below listed information. During the extension

phase ALL adverse events must be recorded on the Adverse Events CRF with the following information:

1. the severity grade [mild, moderate, severe]
2. The relationship to the study treatment (Reasonable possibility that the AE is related: No, Yes)
3. Its duration (start and end dates) or if the event is ongoing an outcome of not recovered/not resolved should be reported at the time of the end of the study
4. whether it constitutes a serious adverse event (SAE)
5. the action taken regarding study treatment
6. whether medication or therapies taken (no concomitant medication/non-drug therapy, concomitant medication/non-drug therapy)
7. the outcome (not recovered/not resolved; recovered/resolved; recovered/resolved with sequelae; fatal; or unknown)

An SAE is defined as any adverse events (appearance of or worsening of any pre-existing condition, undesirable sign(s), symptom(s) or medical condition, which are not protocol endpoints, that meet the following criteria:

- is fatal or life-threatening
- results in persistent or significant disability/incapacity
- constitutes a congenital anomaly/birth defect
- requires inpatient hospitalization or prolongation of existing hospitalization, unless hospitalization is for:
 - routine treatment or monitoring of the studied indication, not associated with any deterioration in condition
 - elective or pre-planned treatment for a pre-existing condition that is unrelated to the indication under study and has not worsened since signing the informed consent
 - treatment on an emergency outpatient basis for an event not fulfilling any of the definitions of an SAE given above and not resulting in hospital admission
 - social reasons and respite care in the absence of any deterioration in the patient's general condition
- is medically significant, i.e. defined as an event that jeopardizes the patient or may require medical or surgical intervention to prevent one of the outcomes listed above
 - In CACZ885M2301, malignancies are considered medically significant. This classification will aid in the data collection on these events.

Study-specific adaption of the standard definition of AEs and SAEs

[REDACTED]
[REDACTED] any cardiovascular
[REDACTED]

event sent for adjudication as a potential study endpoint or reported as a non-adjudicated cardiovascular endpoint by the investigator will not be reported as an adverse event /serious adverse event but will be captured on the Clinical Endpoint Form eCRF. Only if the adjudication committee determines that the event is not a study endpoint, will this event be reported as an adverse / serious adverse event following procedures described in [Section 7.2](#) Serious adverse event reporting.

The study specific exemption does not apply to the extension phase. During the extension phase ALL adverse events will be reported as AEs following the procedures described in [Section 7.1](#) and [Section 7.2](#). No adjudication of events will take place during the extension phase.

Unlike routine safety assessments, SAEs are monitored continuously and have special reporting requirements; see [Section 7.2](#).

All adverse events should be treated appropriately. Action taken may include one or more of the following: no action taken (i.e. further observation only); study drug dosage temporarily interrupted; study drug permanently discontinued; concomitant medication given; non-drug therapy given. The action taken to treat the adverse event should be recorded on the Adverse Event CRF.

Once an adverse event is detected, it should be followed until its resolution or until it is judged to be permanent. - Assessment should be made at each visit (or more frequently, if necessary) of any changes in severity, suspected relationship to the study treatment, interventions required to treat it, and outcome.

[figure not shown]
Information about common side effects already known about the investigational drug can be found in the Investigator Brochure (IB) or will be communicated between IB updates in the form of Investigator Notifications. This information will be included in the patient informed consent and should be discussed with the patient during the study as needed.

The investigator should also instruct each patient to report any new Adverse Experiences (beyond the protocol observation period) that the patient, or the patient's personal physician, believes might reasonably be related to study treatment. This information should be recorded in the investigator's source documents, and if the AE meets the criteria of an SAE, it must be reported to Novartis.

7.2 Serious adverse event reporting

To ensure patient safety, every SAE, regardless of suspected causality, except for those being adjudicated as endpoints or are reported as non-adjudicated cardiovascular endpoint by the investigator during the pivotal phase, which occur after the patient has provided informed consent and until 90 days after the last study visit (following the last administration of study treatment if there are post-treatment follow-up visits) must be reported to Novartis within 24 hours of learning of the occurrence. Any SAEs experienced after this 90 day period should only be reported to Novartis if the investigator suspects a causal relationship to the study drug.

Hypoglycemia events, which require hospitalization or the assistance of another person to treat must, be reported as an SAE.

Information about all SAEs is collected and recorded on the Serious Adverse Event Report Form; all applicable sections of the form must be completed in order to provide a clinically thorough report. The investigator must assess the relationship of each SAE to study drug(s), complete the SAE Report Form in English and submit the completed form within 24 hours to Novartis. Detailed instructions regarding the submission process and requirements for signature are to be found in the investigator folder provided to each site.

Follow-up information is submitted as instructed in the investigator folder. Each re-occurrence, complication, or progression of the original event must be reported as a follow-up to that event regardless of when it occurs. The follow-up information should describe whether the event has resolved or continues, if and how it was treated, whether the blind was broken or not, and whether the patient continued or withdrew from study participation.

[figure not shown]
If the SAE is not previously documented in the Investigator's Brochure or Package Insert (new occurrence) and is thought to be related to the Novartis study drug, a Drug Safety and Epidemiology Department associate may urgently require further information from the investigator for Health Authority reporting. Novartis may need to issue an Investigator Notification (IN) to inform all investigators involved in any study with the same drug that this SAE has been reported. Suspected Unexpected Serious Adverse Reactions (SUSARs) will be collected and reported to the competent authorities and relevant ethics committees in accordance with EU Guidance 2011/C 172/01 or as per national regulatory requirements in participating countries.

Reporting of events (including coincidental cardiovascular events) that are both study endpoints and AE's / SAE during pivotal phase

The integrity of the pivotal phase may be compromised if cardiovascular events that are study endpoints are systematically unblinded in order to fulfill European SUSAR reporting requirements for SAE ([European Commission ENTR/CT12 Guideline \(2006\)](#)). Therefore, in the pivotal phase, potential study endpoints are excluded from the definition of AE's and SAE's and are not to be captured as AE and SAE's but only on the relevant study endpoint CRF. During the pivotal phase, these events are therefore NOT to be reported to Novartis within 24 hours on SAE forms and will not be reported to regulatory agencies or investigators other than as a study endpoint in the Clinical Study Report. Reporting to IRB's should follow local guidelines.

The following pre-defined study endpoints are excluded from the definition of AEs and SAE's in the pivotal phase:

- CV and non-CV Deaths (please see section Reporting of Deaths for specific exceptions for selected non-CV deaths that must be reported as both endpoints AND SAEs)
- Fatal and non-fatal MI
- Fatal and non-fatal Stroke (e.g. hemorrhagic stroke, ischemic stroke)
- [REDACTED]
- [REDACTED]
- Hospitalization or prolongation of hospitalization for heart failure
- Critical Limb ischemia

- Limb amputation
- Transient Ischemia Attack (TIA)
- New onset type 2 diabetes (NOD)
- [REDACTED]
- Coronary angiography / Coronary Revascularization (PCI or CABG)
- [REDACTED]
- [REDACTED]

The Data Monitoring Committee (DMC) will review these endpoint data throughout the pivotal phase in an unblinded manner. Should the DMC make recommendations on the conduct of the pivotal phase that are considered to have significant bearing on the benefit risk of the trial, these will be communicated to competent authorities, IRBs/IECs and investigators and the ECs by Novartis in an appropriate timescale.

Any event that is not listed under the pre-specified endpoints above should be reported as an SAE. If it meets SUSAR criteria, the event will be unblinded; a report to competent authorities and relevant ethics committees and issuance of an IND Investigator Safety Letter will occur per local regulatory requirements.

Should an investigator during the pivotal phase consider that the character and the severity of the above listed events is not consistent with the expected presentation or course of that endpoint and the investigator considers that the study drug may have contributed to this abnormal presentation, then this event should be reported as an SAE and an endpoint.

[figure not shown]
Should an investigator report an SAE during the pivotal phase that is considered by Novartis to be potentially consistent with a study endpoint, Novartis will request confirmation from the investigator that this event is indeed an SAE and not an endpoint. The investigator should respond immediately to these requests in order to minimize the risk that such an event may require unblinding for regulatory reporting of SUSARs. Should the investigator, following this request for review, consider the event to be an endpoint the event must be included as an endpoint and confirmation sent to Novartis DS&E that the event should no longer be considered an SAE. Should the investigator either fail to reply in the necessary timeframe, or confirm that the event is an SAE and not an endpoint, the event will be handled as an SAE.

Events that following data review and adjudication are deemed not to be endpoints for this study will be reported as AEs and SAEs, as soon as adjudication process has been completed, following standard reporting guidelines.

During the extension phase, endpoints will no longer be collected. The above described protocol exemption does not apply for the extension phase. During the extension phase ALL SAEs must be reported to Novartis within 24 hours of learning of the occurrence as outlined in [Section 7.2](#).

[For Japan only]

[In Japan, the following pre-defined study endpoints must be reported to Novartis Pharma K.K within 24 hours of learning of the occurrence, using the “Japan Pre-defined Study

Endpoints Reporting Form". The detail of cases that need to be reported to Novartis Pharma K.K. and procedures for reporting are described in a separate document.

- [REDACTED]
- Hospitalization or prolongation of hospitalization for heart failure
- Critical Limb ischemia
- Limb amputation
- Transient Ischemia Attack (TIA)
- New onset type 2 diabetes (NOD)
- [REDACTED]
- Coronary angiography / Coronary Revascularization (PCI or CABG)
- [REDACTED]
- [REDACTED]

This will not apply to the extension phase.]

[figure not shown]
Reporting of deaths

It is important to note that ALL deaths (deaths considered by the investigator to be CV and non-CV causes) must be reported as predefined study endpoints during the pivotal phase and the investigator must send all documentation for adjudication.

The following SAEs have been causally associated with non-CV deaths due to various medications in the past. Therefore, if a patient during the pivotal phase, is considered to have died as a result of any of the following events, the death must be reported as both an endpoint AND as SAE. The SAE must be reported to Novartis as per SAE reporting guidelines.

NON-CV FATAL EVENTS THAT ARE REPORTED AS BOTH DEATH ENDPOINTS AND SAEs DURING PIVOTAL PHASE

- Allergy events: Anaphylaxis, Angioedema, Laryngeal edema
- Serious hepatic events including hepatic failure, hepatic necrosis, Hy's law case, acute yellow liver atrophy
- Serious cutaneous skin reactions including: Stevens-Johnson syndrome, Toxic epidermal necrolysis, Erythema multiforme
- Drug induced hematological syndromes (including agranulocytosis, aplastic anemia, bone marrow failure, pancytopenia and bicytopenia)
- Inflammatory lung disorders (including allergic, fibrosing, and necrotising alveolitis, eosinophilic pneumonia and interstitial lung disease)
- Autoimmune myocarditis
- Suicide including drug overdose
- Malignant hypertension
- Pulmonary hypertension
- Renal failure (acute and chronic) including tubulointerstitial nephritis
- Hyperpyrexia, Hyperthermia malignant

- Opportunistic infections
- Systemic lupus erythematosus
- Hypoglycemia
- Torsade de pointes, Long QT syndrome
- Pancreatitis
- Drug interaction
- Rhabdomyolysis
- Seizure
- Guillain-Barre syndrome
- Progressive multifocal leukoencephalopathy (PML)

In case the cause of the death event is not listed above it will be reported as study endpoint only. If the death event is adjudicated as a non-CV death, the death event will be reported as serious adverse event.

Reporting of adverse events during extension phase

During the extension phase, endpoints will no longer be collected. The above described protocol exemption does not apply for the extension phase. Therefore ALL adverse events are collected as SAE's, as described in [Section 7.2](#). During the extension phase ALL SAEs must be reported to Novartis within 24 hours of learning of the occurrence.

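### Protocol Section 7.2 tells sites to collect all extension-phase adverse events as SAEs, which contradicts Section 7.1 and the rest of the extension text

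*Protocol*

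**What the plan says.** The text in question is the last paragraph of Protocol Section 7.2, under its own heading on adverse events during the extension. It says that endpoints are no longer collected and that the pivotal-phase exemption no longer applies. It continues: "Therefore ALL adverse events are collected as SAE's", and refers to Section 7.2 for this. The next sentence requires all SAEs to reach the sponsor within 24 hours.

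Section 7.1 gives a different rule for the same phase: "During the extension phase ALL adverse events will be reported as AEs following the procedures described in" Sections 7.1 and 7.2. It has every extension event entered on the Adverse Events CRF with seven attributes, the fourth being whether the event is serious. It defines SAEs as adverse events "which are not protocol endpoints, that meet the following criteria", and then lists those criteria.

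Elsewhere in Section 7.2 the reporting duty covers SAEs only. The opening rule begins "To ensure patient safety, every SAE, regardless of suspected causality". An earlier paragraph on the extension reads "During the extension phase ALL SAEs must be reported to Novartis within 24 hours of learning of the occurrence as outlined in" Section 7.2, and says nothing about all adverse events becoming SAEs.

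**The concern.** The sentence is current operative text, set under the heading where site staff would look for the extension rule. Read as written, a mild, non-serious event in the extension needs SAE handling within 24 hours. Section 11 allows no authorized deviations, so a site that reads it this way could believe it is complying.

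Long-term safety is the main purpose of the extension. The synopsis plans to summarize SAEs separately from AEs, and Section 9.5.3 plans summaries like those of the pivotal phase. If some sites file every event as an SAE and others apply the seriousness criteria, that SAE summary combines two definitions.

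Several usual safeguards are absent. Section 7.5 does not use the DMC in the extension, and Section 7.6 uses no adjudication committee. The SAP does not settle the question, because its introduction leaves extension analyses out. Literal compliance would also add 24-hour reports for events that do not need them.

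**Working it through.** No figure in the plan depends on this sentence, so there is none to reproduce. The check is a comparison of every statement about event collection in the extension.

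| Place in the Protocol | What it requires in the extension |
|---|---|
| Section 7.2, last paragraph | All adverse events are collected as SAEs; all SAEs go in within 24 hours |
| Section 7.1 | All events are recorded and reported as AEs; seriousness is a separate item, judged by listed criteria |
| Section 7.2, earlier extension paragraph | 24-hour reporting for SAEs |
| Synopsis (study design, safety assessments) and Section 3.1 | Both serious and non-serious events are collected |
| Section 6.4.1 | MACE are recorded as adverse events on the AE form |
| Section 7.6.1 | Extension events are reported as adverse events under Sections 7.1 and 7.2 |
| Section 7.3 (extension only) | For an unintentional treatment error, the AE form is used if there is an AE and the SAE form only if there is an SAE |

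The first row stands alone. It cites Section 7.2 as its authority, but nothing else in that section about the extension turns every AE into an SAE. The other rows all require AEs and SAEs to be distinguished.

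The consequence can be set out in symbols. Let *a* be the proportion of patients with any AE, *s* the proportion with an event meeting a seriousness criterion, and *f* the share of patients at sites that follow the last paragraph literally. Assume *a* and *s* are the same at both kinds of site, and that literal sites also mark every event as serious. Then

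reported SAE incidence = *f·a* + (1 − *f*)·*s*, and excess over the true value = *f·(a − s)*.

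- If *f* = 0, the SAE summary shows *s*, as intended.
- If *f* = 1, it equals the AE summary and says nothing about seriousness.
- In between, it is a mixture whose weight is unknown.

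The documents give no value for *a*, *s* or *f* in the extension, so the excess cannot be quantified.

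**The case against.** The strongest reply is that no careful site would take the sentence literally. The SAE definition, the seriousness item, the synopsis, Section 3.1 and Section 7.3 all point the other way. The sentence follows directly on the statement that the exemption has ended, so it was probably meant to say only that former endpoint events now enter ordinary AE and SAE reporting. Section 8.1 requires full verification of SAE documentation, and under Section 8.3 sponsor staff review and query the eCRFs, so misfiled events could be caught. Much of this stands, and it makes wide uptake unlikely. It does not remove the contradiction. The intent is inferred and not stated, and a monitor checking against the Section 7.2 sentence would find such a report compliant.

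A reader might also infer more than the documents support:

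- *That the extension's SAE data would be uninterpretable.* This would need sites to override the seriousness item as well. Where that item is completed by the Section 7.1 criteria, true SAEs can be identified.
- *That SAE incidence would reflect site and not drug.* This implies a drug comparison that is mostly absent. Section 3.4 uses no placebo from Month 9, or from Month 3 after the prediabetes washout. In the short blinded stretch, a site's reading would apply to its patients whatever their arm.
- *That safety is the extension's only aim.* The synopsis calls it the key objective, and Sections 3.1 and 3.2 add the washout question on glycemic status.
- *That the trial's main results are at risk.* Section 8.2 keeps extension data in a separate database, and the sentence governs the extension only.

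**Conclusion.** The point holds as an internal inconsistency in a site instruction, limited to the extension phase. One sentence of Section 7.2 conflicts with Section 7.1 and with every other statement on extension reporting. If some sites follow it, the descriptive SAE incidence could mix two definitions and unneeded expedited reports would be filed. Comparison with pivotal-phase SAE rates, which already needs care because endpoints were exempt there, would become harder.

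The conclusion is conditional on at least some sites following the sentence. Its size is unknown and may be small, given the contrary text and the monitoring. Recovery of true SAEs depends on how the seriousness item was completed. Pivotal-phase efficacy and safety analyses are unaffected by this sentence. The priority is low, but the text is wrong as written.

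**What to change.** Reconcile the last paragraph of Section 7.2 with Section 7.1. Suggested wording: *Therefore all events, including former study endpoints, are collected as AEs per Section 7.1 and, when they meet a seriousness criterion, are reported as SAEs per Section 7.2.*

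In the same edit, clarify the sentence in the pivotal-phase part of Section 7.2 that asks for any event not on the list of pre-specified endpoints to be reported as an SAE. It should say that this means any such event meeting a seriousness criterion. It uses the same loose wording and could be read the same way.

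The cost is two sentences. The design, sample size, forms and planned analyses do not change. Section 11.1 requires a written, approved amendment for any protocol change, so the edit fits best with the next one.
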